## STUDY SUMMARY

Study title:	An Observational Study "FOLLITROPIN" Comparing the Efficacy of Follitropin Alpha Biosimilar: The Real-world Data
Study type:	Phase IV
Test product	
TN: Primapur®
 
INN: follitropin alpha
 
Dosage form: solution for subcutaneous injection
 
Pharmaceutical form: pre-filled disposable syringe containing follitropin alpha 66 µg (900 IU), 33 µg (450 IU), 22 µg (300 IU),
 
Manufacturer: Zavod Medsintez LLC, Russia

Ethical and legal aspects:	
This study conducted in strict accordance with the following international and Russian documents:
 
 
1. Principles of the World Medical Association Declaration of Helsinki (Fortaleza, Brazil, 2013).
 
2. Constitution of the Russian Federation.
 
3. Federal Law "On the fundamentals of protecting the health of citizens in the Russian Federation" dated November 21, 2011 No. 323-FZ, 2011.
 
4. Federal Law "On the Circulation of Medicines" No. 61-FZ dated 12 April 2010.
 
5. Federal Law "On personal data" No. 152-FZ dated July 27, 2006.
 
6. Order of the Ministry of Health of the Russian Federation "On the use of assisted reproductive technologies, contraindications and limitations to their use" No. 107 n dated August 30, 2012.
 

Study goals:	To investigate the efficacy of follitropin alpha biosimilar therapy (Primapur ® ) in nonselected real-world population.
Study objectives:	
The efficacy and safety of biosimilar follitropin alpha have been demonstrated in randomized blinded prospective clinical trials of phases I and III. Unfortunately, there is a gap between the clinical trials and real clinical practice data. The real-world patient data helps to create an evidence-based background for successful implementation of medicine at everyday practice in a nonselected population. The ovarian stimulation (OS) protocols included: monotherapy protocols with using only follitropin alpha biosimilar (Primapur®); mixed protocols (recombinant and urinary-derived gonadotropins) and follitropin alpha biosimilar; short protocols with using antagonists of gonadotropin-releasing hormone (GnRH) and long protocols with

	GnRH agonists. The stimulation protocols were analyzed with Primapur® application for at least 5 days.

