Study design:	Retrospective, observational (non-interventional), anonymized, cohort study
Number of patients	5500 patients
Study centers	35 in vitro fertilization (IVF) clinics in the Russian Federation
Study population:	Women aged 20-43 with established causes of infertility and indications for the use of assisted reproductive technologies (ART) and ovarian stimulation.
Inclusion criteria:	
 
1. Women with established causes of infertility and indications for the use of ART methods, according to the Order of the Ministry of Health of the Russian Federation "On the use of assisted reproductive technologies, contraindications and limitations to their use" No. 107 n dated August 30, 2012.
 
2. Infertility due to female and/or male factor.
 
3. Presence of ovaries accessible for aspiration of follicles.
 
4. Anatomical and functional capability of uterus to bear pregnancy.
 

Exclusion criteria:	
 
1. Women with established contraindications to the use of ART methods, according to the Order of the Ministry of Health of the Russian Federation "On the use of assisted reproductive technologies, contraindications and limitations to their use" No. 107 n dated August 30, 2012.
 
2. Presence of pregnancy
 
3. Hypersensitivity to follitropin alpha and other gonadotropins or excipients.
 
4. Ovarian cysts (not associated with polycystic ovarian syndrome), uterine hemorrhage of unclear etiology
 
5. Premature ovarian failure
 
6. Presence of clinically significant systemic disease
 
7. Presence of chronic cardiovascular, hepatic, renal or pulmonary disease
 
8. Neoplasia
 
9. Narcomania, alcoholism
 

Dosage and duration of treatment; route of administration:	
Drug: Follicle Stimulating Hormone/Luteinizing Hormone
 
Overall ovarian stimulation protocols with follitropin alpha biosimilar for at least 5 days (100-300 IU) and other recombinant follitropins and menotropins, short (antagonists of GnRH) or long protocols (agonist of GnRH).

Concomitant therapy:	All patients received approved medication by physician, accordingly to National guidelines.

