
Efficacy evaluation criteria:
	
Study endpoints per patient:
 
Primary point:
 
 
• Total number of aspirated oocytes.
 
• Incidence of clinical pregnancies (up to 6 weeks after the embryo(s) transfer).
 
 
Secondary points:
 
 
• Number of mature oocytes (MII stage).
 
• Number of fertilized oocytes (zygotes with 2PN).
 
• Total dose of a follitropin alpha biosimilar injected (IU).
 

Safety evaluation criteria:
	
 
• Incidence of serious adverse events e.g., severe ovarian hyperstimulation syndrome (%) with hospitalization.
 
• Incidence of the adverse event, such as injection site pain (%).
 

Groups/arms to compare:
	
 
1. Monoprotocols: follitropin alpha biosimilar only and antagonists/agonists of GnRH (The ovarian stimulation (OS) protocols included monotherapy protocols with using follitropin alpha biosimilar only and antagonists/agonists of gonadotropin-releasing hormone (GnRH): ganirelix, cetrorelix, triptorelin, buserelin).
 
2. Mixed protocols: recombinant and urinary-derived gonadotropins and antagonists/agonists of GnRH. (The OS protocols included: mixed protocols (recombinant with addition of urinary-derived gonadotropins) and antagonists/agonists of GnRH (ganirelix, cetrorelix, triptorelin, buserelin), where follitropin alpha biosimilar used for at least 5 days during OS).
 
3. Monoprotocols: follitropin alpha biosimilar only and antagonists of GnRH (The OS protocols included: monotherapy protocols with using only follitropin alpha biosimilar and antagonists of GnRH).
 
4. Monoprotocols: follitropin alpha biosimilar only and agonist of GnRH (The OS protocol included: monotherapy protocols with using only follitropin alpha biosimilar and agonists of GnRH).
 
5. The overall protocols (The OS protocols included: (1) Monoprotocols: follitropin alpha biosimilar only and antagonists/agonists of GnRH, (2) Mixed protocols: recombinant and urinary-derived gonadotropins and antagonists/agonists of GnRH).
 

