	
Flow chart:
 <pre> graph TD     A[Overall protocols] --> B[Monoprotocols]     A --> C[Mixed protocols]     B --> D[Monoprotocols with antagonist GnRH]     B --> E[Monoprotocols with agonist GnRH] </pre>

Outcome Measures:
	
Primary outcomes:
 
 
1. Number of Oocytes Retrieved
 
2. Percentage of Participants With Ongoing Clinical Pregnancy Per Embryo Transfer
 
 
Secondary outcomes:
 
 
1. Number of Mature Oocytes
 
2. Number of Fertilized Oocytes
 
3. Total Dose of Follitropin Alpha Biosimilar Protocol
 

Groups/Arms to compare
	
 
1. Mixed protocols: recombinant and urinary-derived gonadotropins and antagonists/agonists of GnRH AND Monoprotocols: follitropin alpha biosimilar only and antagonists/agonists of GnRH
 
2. Monoprotocols: follitropin alpha biosimilar only and antagonists of GnRH AND Monoprotocols: follitropin alpha biosimilar only and agonist of GnRH
 
3. Overall protocols – descriptive statistics for all in vitro fertilization protocols
 

Statistical processing of data:
	
Description of methods of statistical data processing
 
The quantitative data obtained during the study will be tested for normal distribution, using the Shapiro-Wilk test and, if necessary, the F-test of equality of variances. For variables corresponding to the normal distribution, mean values and standard deviation of the mean will be calculated; Quantitative data not corresponding to the normal distribution will be described using the median and interquartile interval. Qualitative variables will be described using absolute and relative frequencies (percentages).

In order to compare two groups of normally distributed quantitative data, the Student's t-test will be used; if quantitative data distribution differs from normal values, the Mann-Whitney U test will be used. For intergroup comparisons by qualitative characteristics, the Fisher's exact test will be used.

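### Both between-protocol comparisons rest on unadjusted two-sample tests at p<0.05, so a protocol effect cannot be told apart from a difference in case mix

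*Combined protocol and SAP*

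**What the plan says.** All references are to the Study Summary of the combined protocol and SAP.

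- **Title and design.** The title describes the study as "Comparing the Efficacy of Follitropin Alpha Biosimilar: The Real-world Data". The Study design row reads "Retrospective, observational (non-interventional), anonymized, cohort study".
- **Population.** 5500 patients from 35 clinics: "Women aged 20-43 with established causes of infertility". The inclusion criteria admit "Infertility due to female and/or male factor". The exclusions, such as "Premature ovarian failure", narrow the cohort but leave a wide range of prognosis.
- **Comparisons.** The second Groups/Arms to compare row lists two contrasts: (1) mixed protocols against monoprotocols; (2) within monoprotocols, GnRH antagonist against GnRH agonist. Only the third item, all protocols together, is labelled descriptive. The monoprotocol arm of contrast 1 is "Monoprotocols: follitropin alpha biosimilar only and antagonists/agonists of GnRH", so it pools both analogue types; the mixed arm does too.
- **Tests.** Under Statistical processing of data, normally distributed quantities get Student's t-test; otherwise "if quantitative data distribution differs from normal values, the Mann-Whitney U test will be used". Qualitative variables get Fisher's exact test. Shapiro-Wilk and F-tests serve only as distribution checks.
- **Threshold.** Applicable significance level sets two-sided p<0.05.

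**The concern.** None of the three tests conditions on anything. In a randomised trial the design makes the groups comparable in expectation. Here nothing does, and the documents give no rule for who received which protocol. Women in the two arms may therefore differ in age or cause of infertility. In contrast 1 they may also differ in analogue type, which the plan itself treats as worth testing in contrast 2.

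A p-value below 0.05 could then reflect the protocol, the patients or both, and no planned step separates these. This affects both tested contrasts on both primary outcomes, in a study presented as a comparison of efficacy. A sample of 5500 does not help: it narrows the standard error around a difference that may be confounded.

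**Working it through.** **Step 1: search for any control of confounding.** The Study Summary names no covariate, regression model, propensity score, matching, weighting, stratification, centre term, baseline-balance check or sensitivity analysis for confounding. There is no planned figure to reproduce: 5500 comes without power, effect size, SD or group split.

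**Step 2: inputs for an illustration.** From the documents: N = 5500 and two-sided α = 0.05. Assumed: SD of 6 oocytes; pregnancy proportion 40% in the larger group; 70–100% of patients with a transfer; the group splits; and the shift δ caused by case mix alone. The true protocol effect is set to zero.

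**Step 3: oocytes.** SE = 6·√(1/n₁ + 1/n₂), and P(p<0.05) = Φ(δ/SE − 1.96) + Φ(−δ/SE − 1.96).

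Example, 2750/2750: SE = 6·√(2/2750) = 0.162; 0.6/0.162 = 3.71; Φ(3.71 − 1.96) = 96.0%.

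| Contrast | Split | SE | δ = 0.6 (0.10 SD) | δ = 0.1 |
|---|---|---|---|---|
| 1 | 2750/2750 | 0.162 | 96.0% | 9.5% |
| 1 | 4400/1100 | 0.202 | 84.3% | 7.8% |
| 1 | 5225/275 | 0.371 | 36.6% | 5.8% |
| 2 | 2200/2200 | 0.181 | 91.3% | 8.6% |
| 2 | 3520/880 | 0.226 | 75.6% | 7.3% |
| 2 | 1375/1375 | 0.229 | 74.6% | 7.2% |
| 2 | 2200/550 | 0.286 | 55.5% | 6.4% |
| 2 | 3960/440 | 0.302 | 51.2% | 6.3% |
| 2 | 2475/275 | 0.381 | 35.0% | 5.8% |

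Contrast 2 lies inside the monoprotocol group, taken here as 2750 or 4400 patients with an antagonist share of 50–90%.

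**Step 4: pregnancy.** With s₀ = √[p̄(1−p̄)(1/n₁+1/n₂)] and s₁ = √[p₁(1−p₁)/n₁ + p₂(1−p₂)/n₂], P ≈ Φ((δ − 1.96·s₀)/s₁); the opposite tail is added and matters only for small shifts.

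Example, 40% vs 36%, 1925/1925 (70% of 2750 per group): s₀ = 0.01565, s₁ = 0.01563; (0.04 − 0.03067)/0.01563 = 0.597; Φ = 72.5%.

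| Contrast | Patients before the transfer fraction | 4-point shift | 1-point shift |
|---|---|---|---|
| 1 | 2750/2750 | 72.5–86.4% | 9.7–11.8% |
| 1 | 4400/1100 | 53.0–68.3% | 7.9–9.2% |
| 2 | all six splits above | 18.6–78.0% | 5.7–10.4% |

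Each range runs from 70% to 100% of patients with a transfer.

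**Step 5: the plan's own tests (contrast 1 only).** Mann-Whitney on negative-binomial counts (means 10 and 9.4, SD 6, 1500 runs) rejects in 99.0% of runs at 2750/2750 and 92.3% at 4400/1100. Fisher's exact test, 40% vs 36% (2000 runs), rejects in 69.6% at 1925/1925 and 54.4% at 3080/770. The approximation is not inflating the picture materially.

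**Step 6: would adjustment work?** Simulation with N = 5500 and 400 runs: one measured prognostic factor lowers the mean from 10 to 7 oocytes (negative binomial, dispersion 3), with no protocol effect. Prevalence of 30% vs 50% implies a shift of 0.20 × 3 = 0.6 oocytes; 30% vs 40% implies 0.10 × 3 = 0.3. The adjusted model is linear with robust SE.

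| Split | Prevalence | Mann-Whitney rejects | Adjusted model rejects |
|---|---|---|---|
| 70/30 | 30% vs 50% | 92% | 5% |
| 70/30 | 30% vs 40% | 39% | 5% |
| 85/15 | 30% vs 50% | 73% | 5% |
| 85/15 | 30% vs 40% | 24% | 3% |

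With equal prevalence both methods stay near 5%. Adjustment removes the part of the bias due to measured factors, and only that part.

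**The case against.** The best defence is that the stated goal is broad: efficacy of the biosimilar in an unselected population. Every group receives the biosimilar, the pooled group that answers this goal most directly is descriptive, and no causal or superiority hypothesis is written down. An unadjusted test is a valid test of association between observed groups. This limits the scope to the two contrasts and leaves the overall description untouched. It does not rescue the contrasts, which carry tests and a significance threshold under a title that announces a comparison of efficacy.

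Four narrower points stand:

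- The illustration depends on its assumptions. Small shifts stay near the nominal 5%, a very unequal split cuts the 0.6-oocyte figure to 36.6%, and the monoprotocol group could be smaller than assumed.
- Analogue type can be seen as part of the regimen as delivered, so adjusting for it in contrast 1 is a choice of question that the plan should state.
- Mixed protocols are defined by the addition of urinary gonadotropins, without saying when or why. If the addition came during stimulation, baseline covariates would not remove that selection.
- Exact age may have been used for eligibility at the clinic and not carried into the anonymised file.

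**Conclusion.** The concern holds. Followed as written, the plan declares significance for two non-randomised contrasts with no means of separating protocol from case mix, on both primary outcomes. That follows from the text and needs no numerical assumption.

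The size of any bias is unknown, because there are no baseline data by group. Under the assumptions above and no true effect, a shift of 0.6 oocytes is declared significant with probability 35.0–96.0% across the splits shown. A 4-point pregnancy shift gives 18.6–86.4% across the splits tabulated. Shifts of 0.1 oocytes or 1 point give 5.7–11.8%. The danger lies in moderate imbalances, chiefly where the groups are large and not very unequal. The documents do not show that such an imbalance exists; the defect is that the plan could not deal with one. It needs correcting before either contrast is interpreted.

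**What to change.** In Statistical processing of data:

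1. Make covariate-adjusted models the main analysis of both contrasts: negative-binomial regression for oocyte counts and logistic regression for pregnancy. Inverse-probability weighting on the same variables is an acceptable alternative.
2. Adjust for age as a continuous variable and, in contrast 1, for analogue type, stating that the comparison is meant at a common analogue mix. Add infertility cause, coded clinic, ovarian-reserve markers, BMI and previous cycles where the records hold them.
3. Report covariate-standardised differences in mean oocytes and in pregnancy proportion, each with a 95% CI.
4. Name one pregnancy outcome and denominator for the model. Efficacy evaluation criteria (clinical pregnancy, per patient) and Outcome Measures (ongoing clinical pregnancy, per transfer) differ. This is a separate defect, but the model cannot be specified until it is settled. If transfers are the denominator, state that baseline adjustment does not repair conditioning on a post-treatment event.
5. Keep the t, Mann-Whitney and Fisher results as unadjusted descriptive output. Word conclusions as associations, with residual confounding stated, including possible selection into mixed protocols during stimulation.
6. If adjustment is not possible, label both contrasts descriptive and drop the significance claims.

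**Cost.** SAP wording and modest modelling. Age and analogue type must have been known to apply the age range and form the groups, although it should be confirmed that age is in the analysis file. The documents do not say whether the other covariates are held. The descriptive option costs wording only.

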**Applicable significance level**

In this study, the indicators are considered statistically significant at the bilateral p-value level  $<0.05$ .
